8.9.2 Information bias

Missing data

Missing data can bias the descriptions if data are not missing completely at random . The use of an eCRF that includes online checks for missing information and remote monitoring may reduce the risk of missing data (by limiting to non-existing information and exclude non-reported information).

The use of a mobile application, comprising automatic push notifications, as a tool for filling-in questionnaires (PedsQL) may limit missing data related to PROs.

Social desirability bias

With regard to HRQoL, the social desirability bias refers to the fact that patients may respond to questionnaires in the direction they perceive area of interest, notably to minimize their actual health status severity to please their treating physician. However, we consider this bias to be limited by requiring that completion of questionnaires be done independently from physicians.

8.9.3 Other bias

Another bias may occur by the omission of a variable from a regression model referred as the omitted variables bias. In this study, regression and mixed models will be developed to assess the explanatory endpoints: identify explanatory variables for HRQoL and long-term height evolution. This bias will be mitigated by conducting a literature review to identify all potential factors influencing HRQoL and long-term height evolution, which will be validated by the scientific committee. We expect that most of relevant variables be collected in this study.

8.10 Other aspects

Not applicable.

9 Protection of human subjects

The study will be conducted in accordance with GPP of the International Society for Pharmacoepidemiology (ISPE) Guidelines (5), applicable regulatory requirements, and in accordance of the Declaration of Helsinki.

9.1 Informed consent form for study patients

This non-interventional study will be conducted under the French reference methodology MR-003 “Research in the Field of Health Without Collection of Consent “ updated on May 3th,2018 by the deliberation n°2018-154, which does not require explicit consent but individual patient information.

Novo Nordisk or ██████ undertakes to inform the patients concerned about the processing of personal data within this study in agreement with the General Data Protection Regulation (EU) 2016/679. They will develop and make available to the physicians, an information notice to be given to patients, their parents and/or LAR as the patients may not be of legal age. It is the responsibility of the physicians to inform subjects on the objectives, methods and benefits expected from the study. Subjects will also be informed on their rights to oppose their participation in the study, as well as to access or to correct their data via their physician, should they choose to participate.

The physician must give the patient and/or the patient’s LAR information in a form that the patient or the patient’s LAR can read and understand. This includes the use of impartial witness where required.

In obtaining and documenting non-opposition to data collection, the physician must comply with the applicable regulatory requirement(s) and adhere to the requirements in the Declaration of Helsinki (6).

The task of information can only be performed by the physician or another medically qualified person delegated by the physician, if permitted by local regulation, who must document the patient information and non-opposition on the medical record.

9.2 Data handling

If the patient, the parent or LAR oppose to their participation over the course of the study, the patient's data will be handled as follows:

- Data collected will be used as part of the statistical analysis
- Safety events will be reported to Global Safety, Novo Nordisk and health authorities.

Data will be collected and handled in accordance with local law and IRB/IEC procedures, Institutional Review Boards/Independent Ethics Committee, health authorities and other relevant national institutions/bodies.

Study specific documentation (*for example study protocol, Patient Information/ patient materials*) must be submitted to the relevant national bodies as required by national regulation and procedures in the participating countries.

In France, this study must be approved by the following relevant national bodies :

- The French Data Protection Agency – CNIL: This study will be declared to the CNIL under MR-003 . This declaration is immediate and no waiting time for approval is required. A Privacy Impact Assessment (PIA) shall be developed and submitted to the CNIL.
- The French Medical Council – CNOM: Study investigators will receive a compensation for their participation in the study. Financial agreements to be signed with investigators and study documents (synopsis, protocol and CRF) will be submitted for approval to CNOM (section L. 4113-6 of the Public Health Code).
- The Committee for Protection of Persons-CPP. This study must be approved by the CPP prior enrolling patients in agreement to with the French Law (article L. 1123-6 of the French Public Health Code).

Besides, the protocol, CRF and study reports after completion of the study must be submitted to the HAS as this study aims to address HAS’s information requests regarding the use of Norditropin® for short stature due to NS (long-term effectiveness, safety, quality of life of patients etc.).

In accordance with regulatory requirements, including GVP, the sponsor will inform the health authorities of Norditropin® related adverse reactions. In certain situations, other adverse events may be subject to expedited reporting, if required by health authorities. In addition, the sponsor or ██████████ will inform ANSM (or other appropriate bodies as required locally) of Norditropin® related serious adverse reactions, in accordance with the local requirements in force.

9.3 Premature termination of the study

The sponsor may decide to stop the study or part of the study at any time.

An unplanned termination of the study could occur if any serious safety issue arises with the use of Norditropin® in the study population assessed. If a study is prematurely terminated or suspended, information must be provided to the relevant national bodies as required by national regulation and procedures.

9.4 Responsibilities

██████████ is accountable for the conduct of the study. The conduct and management of the study is performed according to French regulations, Novo Nordisk standard operating procedures (SOPs) and the Project Management Plan (PMP) validated by the Sponsor.

The medical care given to, and medical decisions made on behalf of, patients should always be the responsibility of a qualified physician.

The physician must take all necessary technical and organisational safety measures to prevent accidental or wrongful destruction, loss or deterioration of data. The physician must prevent unauthorised access to data or any other processing of data against applicable law.

10 Management and reporting of adverse events/adverse reactions

10.1 Collection of adverse events and other safety information

Safety definitions and a guideline for evaluation of outcome, severity and causality can be found in appendix A.

All adverse events including all fatal outcomes on Norditropin® which occur after informed consent is obtained and until the follow-up visit/end of study visit must be collected and reported to Novo Nordisk.

If the physician becomes aware of events of overdose, abuse, misuse, medication errors, lack of therapeutic effect or occupational exposure related to the study product treatment with or without an associated suspected adverse reaction, this should be reported to NN on the NIS Safety Form and on the medication error, misuse and abuse form. These events will be summarised by NN in the interim and final study reports.

For female patients: Pregnancies and pregnancy outcome should be collected including **adverse events** in the pregnant patient, foetus or newborn infant from birth to 1 month of age.

For male patients' pregnant partners effort should be made to collect information about the pregnancy and any **adverse reactions and serious adverse events** in the foetus or newborn infant from birth to 1 month of age. Before collecting any information an ad-hoc informed consent form should be signed by the pregnant partner.

For infants exposed to a medicinal product via breast milk, suspected **adverse reactions** (serious and non-serious) should be collected and reported.

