8.1.1.2 Secondary endpoints

Secondary objective-1: To evaluate the long-term safety profile of Norditropin®.

All drug related adverse reactions (ADR), serious adverse drug reactions (SADR), serious adverse events (SAE) and adverse events (AE) will be recorded and described up to the end of growth development or end of follow-up if earlier. The endpoints related to the secondary objective-1 are listed in [Table 3](#).

Table 3 Secondary endpoints in relation to secondary objective 1

Title of endpoint	Time frame	Unit
Number of adverse drug reactions (ADR)	From start of Norditropin® until end of follow-up	Count of events
Number of serious adverse drug reactions (SADR),	From start of Norditropin® until end of follow-up	Count of events
Number of serious adverse events (SAE)	From start of Norditropin® until end of follow-up	Count of events
Number of adverse events (AE)	From start of Norditropin® until end of follow-up	Count of events

Secondary objective-2: To describe the socio-demographic and clinical characteristics of patients. The endpoints related to the secondary objective-2 are listed in [Table 4](#).

Table 4 Secondary endpoints in relation to secondary objective 2

Title of endpoint	Time frame	Unit
Socio-demographic		
Education	From start of Norditropin® treatment until end of follow-up	NA
School level	From start of Norditropin® treatment until end of follow-up	NA
Educational measures	From start of Norditropin® treatment until end of follow-up	NA
Clinical characteristics		

Title of endpoint	Time frame	Unit
Tanner stage	At all visits	NA
Change in pulse rate	From start of Norditropin® treatment until end of follow-up	Beats per minute
Change in diastolic blood pressure	From start of Norditropin® treatment until end of follow-up	mm Hg
Change in systolic blood pressure	From start of Norditropin® treatment until end of follow-up	mm Hg
Change in corrected QT-interval (Electrocardiogram)	From start of Norditropin® treatment until end of follow-up	msec
Change in echocardiogram parameters	From start of Norditropin® treatment until end of follow-up	mm (Left ventricular interventricular septal maximum thickness in diastole) mm (Left ventricular end diastolic diameter) % (Left Ventricular Fractional Shortening (LVFS)) % (Left Ventricular Ejection Fraction (LVEF)) Cm/s (Diastolic function (Ea)) Cm/s (Diastolic function (Aa))

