8.2.8.2 Study visits

The physician should keep a patient enrolment log. The routine treatment of the patients enrolled into the registry should not be influenced by recruitment. Therefore, the data collected is only what is collected as part of standard routine and missing data is expected. This registry will collect data on patients during biannual visits (every 6 months) for 4 years, with possibility of extension for patients who did not reach adult height, starting from the inclusion (D0). As so 8 follow-up study visits (M6; M12; M18; M24; M30; M36; M42; M48) are anticipated. The frequency of the visits is based on actual recommendations on the follow-up of NS patients treated with GH therapy for short stature. Nevertheless, this frequency remains determined by the study site/enrolling physician.

D0 (Baseline-Inclusion)

At the initial visit, children and/or their parents will be informed about the registry objectives and overall requirements, and an information notice will be given to them by the enrolling physician. If they do not oppose to the collect and process of their medical data and are eligible to the registry, the physician will enrol the patient to the study and collect his/her data. Medical data will be collected by physicians using an electronic case report form (eCRF) for each patient. QoL data are patient reported outcomes (PROs) and as so will be collected directly from patients using a questionnaire.

Follow-up visits (from M6 until M48 every 6 months)

During follow-up visits, enrolling physicians will assess patients within clinical routine standard of care. QoL data will be collected annually (D0, M12, M24, M36 and M48) on incident patients.

All drug related adverse reactions (ADR), serious adverse drug reactions (SADR), serious adverse events (SAE) and adverse events (AE) will be recorded and described up to the end of growth development or end of follow-up, if earlier.

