Frequency of injections per week	Categorical variable 
 • 6 days/7 • 7 days/7 • Other 	Endpoints
Type of treatment modifications	Categorical variable 
 • Increase in dosage • Decrease in dosage • Temporary stop • Permanent stop 	Endpoints
Duration of temporary stop	Continuous variable	Endpoints
Number of treatment modifications	Categorical variable 
 • From 1 to 5 	Endpoints
Reasons for treatment modifications	Categorical variable 
 • Safety (occurrence of ARs or AEs) • Growth too fast • Growth too slow • Patient's or parents/LAR choice • Other 	Endpoints
Type of previous GH treatments	Categorical variable	Endpoints
Dose of previous GH treatment at start	Continuous variable	Endpoints
Total duration of previous GH treatment	Continuous variable From start of previous GH treatment until the end of treatment	Endpoints
Type of GH treatment following Norditropin®	Categorical variable	Endpoints
Dose of GH treatment following Norditropin®	Continuous variable	Endpoints
Date of GH treatment following Norditropin®	Continuous variable	Endpoints
Concomitant medications	Categorical variable 
 • ADHD medications including methylphenidate • Cardiac medications • Thyroid hormones • Sex steroids including testosterone and oestrogen 	Endpoints

Variables	Operational Definition	Measurement
	
 Other 	
HRQoL		
PedsQL score	Categorical variable 
 From 0 to100 	Endpoints
Safety		
Incidence rate	Number of new cases per population at risk over the follow-up period (per person-time)	Endpoints
Other co-variates (controls)		
Sites 'geographic location	Categorical variable : 
 Ile-De France North-West West East South-East South-West 	Bias
Sites 'activity size s	Continuous variable Defined by the number of children treated with Norditropin® for short stature due to NS managed over a year	Bias

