8.7.4 Sequential safety analysis/safety monitoring

All drug related adverse reactions (ADR), serious adverse drug reactions (SADR), serious adverse events (SAE) and adverse events (AE) will be classified and analysed from the initiation of the study drug until the end of follow-up.

Medical Dictionary for Regulatory Activities (MedDRA) version 19.1 or higher will be used for coding to "Lower Level Term (LLT)", "Preferred Term (PT)", "High Level Term (HLT)", "High Level Group Term (HLGT)" and the associated primary "System Organ Class (SOC)". CTCAE version 5 will be used to provide the grade.

AEs will be analysed as follows:

The number and percentage of patients experiencing:

- at least 1 on-treatment SAE/AE/SADR/ADR (including non-serious and serious irrespective of the relationship with the study treatment)
- at least 1 on-treatment SAE/AE/SADR/ADR related to the study treatment (including serious and non-serious AEs)
- at least 1 on-treatment serious SAE/SADR (regardless the relationship with the study treatment)
- at least 1 on-treatment serious SAE/SADR related to the study treatment
- at least 1 on-treatment SAE/AE/SADR/ADR leading to treatment discontinuation
- at least 1 on-treatment SAE/AE/SADR/ADR leading to treatment interruption/delay
- at least 1 on-treatment SAE/AE/SADR/ADR leading to dose decrease
- fatal on-treatment SAE/AE/SADR/ADR

They will be presented by SOC and preferred term.

Patient will be counted once by AE taking into account the maximum grade. The SOC/PT will be summarized (irrespective of the grade) and by maximum grade CTCAE (grade 1-2 ,3-4 and 5) as well. The incidence rate, corresponding to the number of patients experiencing at least one AE divided by the total person years of follow-up, will be calculated for each AE. A listing will be provided for fatal on-treatment AE. These analyses will be performed for the post-treatment AEs as well.

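### The protocol gives conflicting adverse-event windows and does not settle whether events before inclusion are collected, although about 86% of planned patients are prevalent

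*Protocol*

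**What the plan says.** All references are to the protocol.

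**Start of the AE window.** Section 10.1 covers events "which occur after informed consent is obtained and until the follow-up visit/end of study visit must be collected". Section 8.2.9 likewise speaks of events during follow-up, ascertained at each follow-up visit. Table 3 in section 8.1.1.2, however, gives all four AE counts the time frame "From start of Norditropin® until end of follow-up", and section 8.7.4 says that events "will be classified and analysed from the initiation of the study drug until the end of follow-up".

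**End of the window.** The text of section 8.1.1.2 says that events "will be recorded and described up to the end of growth development or end of follow-up if earlier", and section 8.2.8.2 repeats this. Section 10.1 runs to the end-of-study visit. Table 3 and 8.7.4 run to the end of follow-up, and 8.7.4 adds the same analyses for post-treatment events.

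**Consent.** Section 9.1 places the study under a reference methodology "which does not require explicit consent but individual patient information". Patients are informed and may object.

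**Prevalent patients.** Section 8.1 says that those who finished growing before inclusion have all their data taken retrospectively from records since treatment start, and that those still growing have both retrospective and prospective data. It neither names AEs nor excludes them.

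**Denominators.** Section 8.2.9 puts every child with at least one administration into the safety evaluation. Section 8.7.4 defines the incidence rate as patients with at least one event "divided by the total person years of follow-up, will be calculated for each AE". Table 10 refers to person-time over the follow-up period. Neither says when the clock starts for a prevalent patient.

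**The concern.** A rate is interpretable only if events and exposure cover the same period. The sections telling sites what to collect (10.1, 8.2.9) describe capture after entry, while those telling the analyst what to summarise (Table 3, 8.7.4) start at the first dose. For an incident child the two starts nearly coincide. For a prevalent child they may be years apart.

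If sites follow 10.1 and the analysis follows 8.7.4, prevalent patients can bring treated years into the denominator without the events of those years in the numerator. The error would then run towards too few events.

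Long-term safety is the first secondary objective, and the registry was requested partly for safety information, notably on tumours, glucose metabolism and cardiac defects. Events that were never abstracted cannot be restored by an analysis plan, so the protocol and the case report form have to settle this.

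**Working it through.** **1. The windows side by side**

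| Section | Start | Stop |
|---|---|---|
| 10.1 | informed consent | follow-up / end-of-study visit |
| 8.2.9 | during follow-up | during follow-up |
| 8.1.1.2 text, 8.2.8.2 | not stated | end of growth, or end of follow-up if earlier |
| 8.1.1.2 Table 3 | treatment start | end of follow-up |
| 8.7.4 | treatment start | end of follow-up, plus post-treatment analyses |
| 8.1 (prevalent, data in general) | treatment start | not specific to AEs |

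These cannot all hold. The start in 10.1 also lacks a matching event, because section 9.1 requires no explicit consent from registry patients.

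**2. How many patients are affected**

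Inputs from section 8.5: 50 eligible incident patients, at most 30 prevalent per year since 2010, 79% of sites participating, 80% of eligible patients included. Ten start years (2010–2019) reproduce the protocol's total:

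(50 + 30 × 10) × 0.79 × 0.80 = 221.2, stated as 221.

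- Incident: 50 × 0.79 × 0.80 = 31.6
- Prevalent: 300 × 0.79 × 0.80 = 189.6
- Prevalent share: 300/350 = 86%

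**3. Size of the dilution on the unfavourable reading**

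This reading takes events only from inclusion but counts person-years from treatment start. Two inputs are assumptions, because the protocol gives neither:

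- L, the mean treated years before inclusion of prevalent patients
- f, the share of prevalent patients who have finished growing and contribute no observed time

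Every other patient is given 4 observed years (the planned follow-up), and the event rate is taken as constant.

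Observed person-years = 31.6 × 4 + 189.6 × (1 − f) × 4

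Counted person-years = observed + 189.6 × L

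Reported rate / true rate = observed / counted

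For L = 4, f = 0.5: observed = 126.4 + 379.2 = 505.6; counted = 505.6 + 758.4 = 1,264; ratio = 0.40.

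| f | L = 1 | L = 2 | L = 4 | L = 8 |
|---|---|---|---|---|
| 0 | 0.82 | 0.70 | 0.54 | 0.37 |
| 0.5 | 0.73 | 0.57 | 0.40 | 0.25 |
| 1 (extreme) | 0.40 | 0.25 | 0.14 | 0.08 |

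**4. The favourable readings**

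If person-time starts at inclusion, the pre-inclusion term drops out and the ratio is 1. If pre-inclusion events are abstracted completely, events and time again share one window and the ratio is 1.

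Percentages behave differently. If person-time starts at inclusion but earlier events are not taken, finished-growth patients add no prospective time yet stay in the patient denominator under 8.2.9. At f = 0.5 that is 94.8 of 221.2 patients (43%).

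**The case against.** The strongest reply is that the protocol already plans retrospective collection. Section 8.1 promises all data from treatment start for finished-growth patients and both kinds of data for the others, without exempting AEs. Section 10.1 sits in the safety-reporting chapter and sets what must be reported; it does not forbid abstracting earlier events. This stands, so a reader who infers that no pre-inclusion event could be recorded goes too far. It does not remove the conflict, since no AE-specific section carries the general statement through.

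A reader might also infer an AE window of zero length for children who had finished growing. That comes from joining the start in 10.1 to the stop in 8.1.1.2 and 8.2.8.2. No section states that combination, and 10.1 itself contradicts a stop at end of growth.

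It is also fair to say that dilution is not shown. The rate definitions refer to follow-up, and section 8.2.8.2 describes 4 years of visits starting at inclusion. On that reading pre-inclusion years never enter the rate. Detailed person-time rules may properly sit in an analysis plan that is not shown.

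Three lesser points stand:

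- The absence of a baseline safety entry in Table 9 proves little. Section 8.1 gives the M0–M48 schedule for incident patients, who are only then starting treatment.
- The case report form is a separate document, so it may already hold a retrospective AE page.
- HbA1c, fasting glucose, QTc and echocardiography are separate endpoints and do not depend on the AE window.

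**Conclusion.** The protocol contradicts itself on when AE collection starts and stops, and leaves open whether pre-inclusion AEs are abstracted. The contradiction needs no assumption and touches about 190 of 221 planned patients (86%).

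Understated safety figures are a conditional risk. They arise if earlier events are not systematically collected while patients and person-time count from treatment start. Over 1 to 8 pre-inclusion years, the reported rate would then be 0.37 to 0.82 of the true rate with no prevalent patient finished growing, and 0.25 to 0.73 with half finished. These figures illustrate assumed inputs and 4 observed years per remaining patient, so no single factor should be quoted as the size of the error. Nor do the documents support saying that the plan as a whole makes the product look safer: the dilution of rates vanishes if person-time starts at inclusion or retrospective capture is complete.

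Correction is still needed in the protocol. Following 10.1 and 8.2.9 for collection and Table 3 and 8.7.4 for analysis, as written, mismatches events and exposure for most of the registry.

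**What to change.** - Reconcile sections 8.1, 8.1.1.2 (text and Table 3), 8.2.8.2, 8.2.9, 8.7.4 and 10.1 into one AE window, with one start and one stop. State how post-treatment events fit within it.
- Replace informed consent as the start in 10.1 with the inclusion or non-opposition date.
- State explicitly that AEs of prevalent patients are abstracted from treatment start, or that they are not.
- Use the same start and stop for events, patients at risk and person-years.
- Compute the main incidence rate from prospective events over prospective person-time. Report retrospective events separately with their own denominator. Separation is useful even if abstraction is complete, because a child must be under follow-up at a participating centre to be included, so a death before inclusion cannot appear in the retrospective period.

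The cost is protocol wording, some added abstraction from records that are already being read, and fewer person-years in the main rate.
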